5.3.7 Medical Care of Subjects after End of Study

The study is a post-treatment observational study. The participation of the subject in the study will not have any impact on their routine medical care. Consequently, the end of the study will also have no impact on their medical care.

6 Investigational Medicinal Product(s) and Other Drugs Used in the Study

Not applicable – post-treatment observational study.

6.1 Description of Investigational Product(s)

Not applicable - No investigational medicinal product will be administered during this study, which is a post-treatment follow-up of subjects previously treated with Saizen® or other r-hGH products. The dose and mode of administration of previous r-hGH treatments are those established by the approved prescribing information for each product.

6.2 Dosage and Administration

Not applicable – post-treatment observational study.

6.3 Assignment to Treatment Groups

Not applicable – post-treatment observational study.

6.4 Other Drugs to be used in the Study

Not applicable – post-treatment observational study.

6.5 Concomitant Medications and Therapies

6.5.1 Permitted Medicines

All therapies and medications are allowed during the study, except treatment with r-hGH.

6.5.2 Non-permitted Medicines

No therapies or medications are prohibited during the study, except treatment with r-hGH.

6.5.3 Other Study Considerations

None.

6.5.4 Special Precautions

None.

6.6 Packaging and Labelling

Not applicable - post-treatment observational study.

6.7 Preparation, Handling and Storage

Not applicable - post-treatment observational study.

6.8 Investigational Medicinal Product Accountability

Not applicable - post-treatment observational study.

6.9 Assessment of Investigational Medicinal Product Compliance

Not applicable - post-treatment observational study.

6.10 Method of Blinding

Not applicable - post-treatment observational study.

6.11 Emergency Unblinding

Not applicable - post-treatment observational study.

6.12 Treatment of Overdose

Not applicable - post-treatment observational study.

7 Study Procedures and Assessments

7.1 Schedule of Assessments

This is an observational study. Therefore, no study-specific visits are scheduled in the protocol.

Investigators (i.e., paediatricians and/or endocrinologists) who treat at their clinics short children who were born SGA will be responsible for screening and enrolling subjects. Eligible subjects (see also section 5.3.1) include subjects who completed or permanently discontinued treatment with Saizen® or other r-hGH products within 5 years prior to enrolment in the study. Subjects may have been enrolled in previous sponsored clinical studies with r-hGH in the SGA indication or may have received r-hGH products in a post-marketing setting. In any case, subjects (with parents/guardian as applicable) will need to attend first a screening visit in order to sign the ICF and enrol in the study.

During the course of the study, subjects are not required to visit the study Investigator. Subjects may go to their GP or other treating physician for their routine medical visits. Only information gathered by the treating physician/GP from procedures performed as part of the routine clinical practice may be available for the study. The medical data of interest (see Table 1) for this study (when/if available) will be collected by the investigator from the patient's treating physician/GP. Since the treating physician/GP will document the subject's routine medical data considered necessary for the patient's standard medical care, not all the data of interest described in Table 1 may be available to the study Investigator.

In order to minimize the subject loss to follow-up and to maintain subject motivation during the 10 years of the follow-up study, the CRO's dedicated PMC will contact the subjects once a year to update/confirm subjects' and treating physicians' contact information in order to send them the "Yearly Subject and Investigator SALTO kits", and to identify any change in health status/medical history. If any relevant change is identified by the PMC, the PMC will notify the investigator, who will gather the pertinent information from the treating physician/GP. The detailed content of the "Yearly Subject SALTO kit" is addressed in section 10.1.

In order to ensure adequate collection of the post-treatment medical data of interest, the following activities will be performed:

- After every yearly call from the PMC, the PMC will update the contact information of the subject and subject's treating physician in the appropriate databases, and send the "Yearly Subject SALTO kit" to the subject/contact person. In addition, the PMC will identify any relevant change on the subject's health status, and will contact the Investigator who will obtain the relevant medical data from the subject's treating physician as previously described.
- 2. The subject can request a copy of his/her medical history/laboratory results from the treating physician/GP and send it to the Investigator who will enter the information into the electronic case report form (eCRF).
- 3. The Investigator will call the subject 5 and 10 years after r-hGH discontinuation to obtain any additional available relevant medical information.

Data collection will start once subjects have entered the study and will continue for a maximum of 10 years after discontinuation of treatment with Saizen® or other r-hGH products. Prior to collecting any data, the Investigator (i.e. paediatrician/endocrinologist) will ensure that the subject has provided a signed, written ICF according to the procedure described in section 9.2.

For subjects who have entered the study within the 5-year period after r-hGH treatment discontinuation, any data of interest occurring from the time of permanent cessation of r-hGH therapy up to the signature of the ICF will be retrospectively collected and recorded into the eCRF by the Investigator.

Data reporting is allowed at any time if a subject or his/her Investigator reports an adverse event related to changes in glucose metabolism parameters or to malignancy or to any Serious Adverse Event related to r-hGH treatment.

During subsequent follow-up visits, the Investigator or subject's treating physician/GP (when applicable) will ensure that the subject is informed and updated on the study.

Method of Reporting AEs of Interest

At the time of obtaining Informed Consent, the Investigator will explain the process of reporting an AE to the subject. The subject will be provided with a leaflet containing information on the AEs of interest (i.e., type 2 diabetes mellitus, metabolic syndrome and/or changes in glucose metabolism parameters, fasting insulin levels, HbA_{1c}, 2-hour OGTT results, blood pressure, lipid parameters, and parameters related to malignancies) and key message/information of the Company's post-approval commitment (PAC).

If the subject experiences an AE of interest (see definition of AE of interest in section 7.4.1.1) or a serious adverse event (SAE) of interest, the subject or his/her parents/guardians will be asked to call the PMC on the toll-free phone number that is enclosed in the yearly Subject SALTO Kit. The subject will inform the PMC of the AE/SAE details and the contact information of the treating physician. Upon receipt of the information, the PMC will immediately forward the received information to the corresponding Investigator. The Investigator may follow up with the subject and the subject's physician to confirm the received medical information, and determine if the AE/SAE is relevant for this study. This will be followed by reporting the AE/SAE of interest to the CRO/Sponsor by completing an eCRF and an SAE Report Form in case of SAE.

The timelines and methods for reporting these AEs/SAEs of interest by the Investigator are described in section 7.4.1.2.

Table 1 Summary of Data to be Collected*

Time points	Baseline	At any time over 10 years	At year 5	At year 10
Demographic characteristics and r- hGH treatment history	х			
Medical history/relevant change in medical history	х	х	х	х
Familial medical history/ relevant change in familial medical history	Х	х	Х	Х
Anthropometric parameters				
Height (cm)	X	X	X	X
Weight (kg)	X	X	X	Х
Waist circumference (cm)	Х	Х	Х	X
Hip measurement (cm)	Х	Х	Х	X
Occurrence of type 2 diabetes/ glucose metabolism disorders/ metabolic syndrome	х	х	Х	х
Occurrence of malignancies (type, histological result, histological result, location, size, grading, severity, treatment, outcome)	x	х	x	х
Metabolic parameters				
Fasting Plasma insulin	Х	Х	X	х
Fasting Plasma glucose	Х	Х	Х	Х
HbA1c (%)	Х	Х	X	Х
2 hour OGTT	Х	Х	Х	Х
Plasma triglycerides	Х	Х	X	Х
HDL-cholesterol	Х	χ	Х	Х
LDL-cholesterol	Х	Х	Х	Х
Total cholesterol	Х	Х	Х	Х
Blood pressure	Х	Х	Х	Х
Urinary albumin excretion rate	Х	Х	Х	Х
Urinary Albumin:creatinine ratio	Х	Х	Х	Х
Concomitant medications (Only relevant concomitant medications are to be collected as per the Investigator's judgement)	х	х	х	х

^{*} Data to be collected by the Investigator only if available during routine medical care performed by the treating physician/GP

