However, clinical data will be collected by the Investigator on an ongoing basis and when available during the course of this study through the subject's treating physician/GP or when provided directly by the subject/person of contact (see sections 7.1; 9.1; 9.2; 10.1). Additionally, the investigator will contact the subjects at roughly 5 and 10 years after discontinuation of r-hGH treatment in order to obtain any additional available relevant medical information (see section 7.1).

In order to minimize the subject loss during the 10 years of the follow-up study, the CRO's dedicated PMC will contact the subjects once a year to update/confirm subjects' and treating physicians' contact information in order to send them the "Yearly Subject and Investigator SALTO kits", and to identify any change in health status/medical history. If any relevant change is identified by the PMC, the PMC will notify the investigator, who will gather the relevant information from the treating physician/GP (see section 7.1).

The 5-year interim data and 10-year post-treatment data will be analysed (see section 8.6). If possible, correlation of type 2 diabetes mellitus and/or malignancy will be assessed against blood pressure, body mass index, lipid parameters, medical history and familial inheritance studies (see section 8.5).

Thus, it is anticipated that most subjects will participate in the present study between 2020 and 2030 (see Figure 1). First patient in in 2011, last patient in by 2020, and last patient out by end of 2030.

Figure 1 Study Design

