7.4.1.3 Definition of the Adverse Event Reporting Period

The AE reporting period for safety surveillance is defined as the 10-year period after cessation of r-hGH treatment (i.e., during the 10 years after the date of last r-hGH administration).

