7.4.1.4 Procedure for Reporting Serious Adverse Events

In the event of any new SAE related to the previous r-hGH treatment or any SAE of interest (related and not related) occurring during the reporting period, the Investigator must immediately (i.e. within a maximum **24 HOURS** after becoming aware of the event) inform the CRO, PPD, by phone, fax or by email. Non-serious AEs of interest (related and not related) are sent to the CRO within one week. The reports have to be sent by phone, fax or by email to the contact details below:

Email: PPD

Fax: PPD

Safety Hotline: PPD

The CRO, PPD , will check legibility, consistency and plausibility of all AE reports and will forward all these AE reports to the Sponsor (Merck KGaA) within 24 hours. Furthermore, PPD will serve as an interface between the Sponsor and the site/Investigators, and will ensure that queries and follow-up information are managed accordingly.

When an event (or follow-up information) is reported by telephone, a written report must be sent immediately thereafter by fax or email, in the format of a SAE Report Form.

Reporting procedures and timelines are the same for any new information on a previously reported SAE related to r-hGH treatment or SAE of interest (= follow-up).

For names, addresses, telephone and fax numbers for SAE reporting, see information included in the SAE Report Form or the protocol, or as applicable, in a specific document including Sponsor contact details.

All written reports on SAEs should be transmitted using the SAE Report Form, which must be completed by the Investigator following specific completion instructions. Relevant pages from the eCRF may be provided in parallel (e.g., medical history, concomitant drugs). In all cases, the information provided in the SAE Report Form must be consistent with the data on the event that are recorded in the corresponding sections of the eCRF.

The Investigator must respond to any request for follow-up information (e.g. additional information, outcome and final evaluation, specific records where needed) or to any question the Sponsor may have on the AE of interest within the same timelines as described for initial reports. This is necessary to permit a prompt assessment of the event by the Sponsor and (as applicable) to allow the Company to meet strict regulatory timelines associated with expedited safety reporting obligations.

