8.5.2 Analysis of Primary Safety Endpoints

For primary endpoints, details for each subject of the safety population will be listed and will include at least; time on follow-up, onset date(s) of event(s) and description of event(s).

In parallel with numbers and proportions of subjects experiencing the events, the incidence rate per subject-years of follow-up will be calculated during the 10-year follow-up. The subject-time of follow-up will be defined as the time between the day of last r-hGH treatment and the end of the 10-year period. Furthermore, an analysis of association of the primary endpoints with subject characteristics (e.g., age, sex, blood pressure, BMI, family history) and possible confounding factors of the diseases (e.g., concomitant treatment, medical history, environmental factors) will be conducted. Exploratory analysis will be performed by each brand of r-hGH product if permitted by sample size per brand.

Further details will be provided in the SAP.

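### Data collection is capped at the same 10-year date that ends the event window, and the closing contact is only loosely timed, so late events can be missed while the full time is credited

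*Protocol*

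**What the plan says.** Four statements in the protocol fix the end of a subject's follow-up.

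- **Collection window, 7.1:** "Data collection will start once subjects have entered the study and will continue for a maximum of 10 years after discontinuation of treatment".
- **Event window, 7.4.1.3:** "The AE reporting period for safety surveillance is defined as the 10-year period after cessation of r-hGH treatment".
- **Closing contact, 5.1:** "the investigator will contact the subjects at roughly 5 and 10 years after discontinuation of r-hGH treatment". Section 7.1 gives the same contact without the qualifier: "The Investigator will call the subject 5 and 10 years after r-hGH discontinuation to obtain any additional available relevant medical information". The synopsis and 9.1 also omit the qualifier. No section states a window around this contact, requires it on or after the anniversary, or allows a period after year 10 for recording.
- **Subject-time, 8.5.2:** "The subject-time of follow-up will be defined as the time between the day of last r-hGH treatment and the end of the 10-year period".

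Other provisions bear on how an event becomes known.

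- The yearly call in 7.1: "PMC will contact the subjects once a year to update/confirm subjects' and treating physicians' contact information". The same call asks about changes in health.
- Also in 7.1: "Data reporting is allowed at any time if a subject or his/her Investigator reports an adverse event", which covers events of glucose metabolism and malignancy.
- Sections 5.1 and 7.1 provide for ongoing data from the treating physician or the subject, and for a toll-free line.
- Section 7.4.1.4 ties serious events to the date on which they occur: for "any SAE of interest (related and not related) occurring during the reporting period, the Investigator must immediately" inform the CRO.

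**The concern.** The event window and the collection window end on the same day, but knowledge of an event lags behind its occurrence. Under 7.1 a report may pass from the subject to the patient management centre (PMC), then to the investigator, who obtains confirmation from the treating physician before the eCRF is completed. Diabetes diagnosed at 9.8 years and learned of at 10.2 years lies inside the event window and, read literally, outside the collection window. Sites may resolve that differently.

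A closing call at 9.5 years has the opposite problem. It respects the cap, but the last half year is then treated as event-free without having been asked about.

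Any miss acts in one direction. It lowers the numerator of both primary endpoints while the denominator in 8.5.2 stays full. In a single-cohort safety commitment without a control group, that error is towards reassurance. An analysis plan cannot recover data that were never collected.

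**Working it through.** **The plan's own figure.** The protocol gives no figure for this point. Its only computed figure is the enrolment target: 200/(1 − 0.35) = 307.7, so 308, against the stated approximate 300, which is 150% of 200. The point does not depend on it; only the 200 completers are used below.

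**The two cases for the closing call.**

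1. *Call before the anniversary.* Time from the call to 10.0 years is inside the event window (7.4.1.3) and inside subject-time (8.5.2). The yearly PMC call may fall in that gap, but nothing requires it to. Otherwise detection depends on physician data or on the subject reporting.
2. *Call on or after the anniversary.* If it asks about events up to 10.0 years, nothing is lost by timing. A loss arises only if the cap in 7.1 is read as barring the recording of in-window events learned of later.

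**Size in case 1.**

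Inputs:
- Window T = 10 years (7.4.1.3, 8.5.2).
- Completers: 200 (8.1), so 200 × 10 = 2000 credited subject-years.
- Gap g between the closing call and the anniversary: not in the documents. Assumed to be 1, 3 or 6 months.
- Detection by other routes: set to zero, which makes every result an upper bound.

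Formulas, treating events as rare:
- Uncovered share of credited time = g/T.
- Share of events in the gap under a constant hazard = g/T.
- Share of events in the gap if the hazard rises linearly from zero at cessation = 1 − ((T − g)/T)².

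For g = 0.5 years: 0.5/10 = 5%; 1 − (9.5/10)² = 1 − 0.9025 = 9.75%; and 200 × 0.5 = 100 subject-years.

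| Call early by | Uncovered share | Subject-years of 2000 | Events missed at most, constant hazard | Events missed at most, rising hazard |
|---|---|---|---|---|
| 1 month | 0.8% | 16.7 | 0.8% | 1.7% |
| 3 months | 2.5% | 50 | 2.5% | 4.9% |
| 6 months | 5% | 100 | 5% | 9.8% |

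Under a constant hazard, the observed rate divided by the true rate is (10 − g)/10, which runs from 0.992 at 1 month to 0.95 at 6 months.

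**Size in case 2.** Under the literal reading the same formulas apply, with g as the time since the last contact inside the window. No separate figure is given, because it depends on a reading that other sections contradict.

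**The case against.** The cap in 7.1 most naturally describes the period that the data cover, in line with the maximum follow-up in 5.1. Section 7.4.1.2 requires documentation of events of interest experienced during the reporting period. Section 7.4.1.4 makes serious ones reportable within 24 hours of the investigator becoming aware. The any-time sentence in 7.1 covers the domains of both primary endpoints. Section 7.1 also records earlier events retrospectively for late enrollees. The approximate timing appears only in 5.1, nothing says that calls are made early, and contact windows are often left to the analysis plan.

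Much of this stands. A reader might infer that late events are lost; the documents support only that they can be. A loss needs an early call and the failure of every other route, or a restrictive reading of the cap. Nor is contact limited to one call a year.

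A reader might also carry the argument over to the year-5 contact. It fails there: collection continues after year 5, onset dates are recorded, and later contacts can pick up an event from 4.9 years.

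Nor does any section say that a subject last called at 9.5 years is a 10-year completer. The protocol simply does not say how 10-year completion is verified.

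The objection does not remove the conflict. The cap, the approximate timing and the subject-time rule are all stated in the protocol. None of the other routes is expressly said to run beyond year 10, and Table 1 heads its open column as running over 10 years.

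**Conclusion.** The point holds as a conflict between stated rules, with a small possible bias in one direction. An early closing call leaves credited time that may go unobserved. A late one is sound by timing, but sits uneasily with the literal cap.

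For an assumed call 1 to 6 months early, at most 0.8% to 5% of the credited 10 years is uncovered. That is also the ceiling on events missed under a constant hazard; under a linearly rising hazard it is 1.7% to 9.8%. These are not estimates of loss. They assume that every subject is called that early and that no other route reports the event. The gap and the hazard shapes are assumptions, and the true size cannot be derived from the protocol.

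The change is worth making because it is cheap and because late-window data may be unrecoverable once collection closes. A separate and potentially larger weakness is that 8.5.2, as worded, does not end subject-time at dropout, death or event. The figures here do not include it.

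**What to change.** - **5.1 and 7.1:** hold the closing contact on or after the 10-year anniversary, within a stated window (for example 10.0 to 10.5 years), and drop the approximate timing for that contact.
- **7.1:** keep the event window at 10.0 years, but state that events with onset up to that date may be recorded and confirmed afterwards.
- **8.5.2:** end subject-time at the last date of actual ascertainment, at most 10 years.
- **8.1 or 8.5.2:** count a subject as a 10-year completer only if ascertainment reaches 10.0 years.

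The cost is a few sentences and no added visits. Some last contacts may move a few months past the anniversary. A subject whose treatment ended late in 2020 could then be contacted after the end-2030 last-patient-out date in 5.1 and the synopsis. Those dates, the 10-year maximum in 5.1 and the end-of-study definition in 5.3.6 need matching wording. The extra months must also fit the 12 months that 10.6.1 allows for the final report.

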5.1 Overall Study Design and Plan

This study is a prospective and retrospective, single-cohort, multicentre, observational long-term post-approval commitment study in subjects born SGA, with no specific age restrictions, who received Saizen® or other r-hGH products for the treatment of short stature. It is a multinational study that will be performed at up to approximately 40 to 60 sites globally. The study will consist of a 10-year post-treatment safety assessment in subjects who were previously treated with r-hGH and who completed or permanently discontinued r-hGH therapy. Eligible subjects may have been enrolled in sponsored clinical studies or may have received r-hGH products in a post-marketing setting. Subjects may be enrolled at any time from the day after their last r-hGH dose up until 5 years after treatment cessation. The maximum duration of follow-up will be 10 years after treatment cessation. All subjects must have received r-hGH products for the treatment of short stature due to SGA as approved per country product label. There is no control group.

The overall objective is to collect safety data with a primary focus on type 2 diabetes mellitus and malignancies during the 10-year follow-up period after termination of r-hGH treatment in the SGA subjects (see section 4).

The aim is to have a final study population of 200 subjects after 10 years of follow-up for analysis. Approximately 300 subjects will be enrolled at study initiation in order to compensate for anticipated loss to follow-up (see section 8.1).

All subjects must sign the Informed Consent Form (ICF) to be enrolled in the study. Subjects may sign the ICF on the day after r-hGH treatment discontinuation (see section 9.2) and up to 5 years after treatment cessation. Prior to enrolment into the study, subjects who are currently being treated with an r-hGH product may be asked to optionally sign a Contact Information Consent Form (CICF) in order to allow the CRO's PMC to contact the subjects and track subject contact information only (see section 9.2).

Because SALTO is a post-treatment observational study, no scheduled study-specific visits, assessments or interventions are scheduled during the study (see section 7.1).

[figure not shown]

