5.3.2 Exclusion Criteria

Subjects are not eligible for this study if they fulfil any of the following exclusion criteria:

- Patients unwilling and/or parents/guardians who are not capable of ensuring compliance with the study protocol.
- Patients enrolled in an interventional trial
- Patients enrolled in an observational trial of a similar nature to the SALTO study, where the
 protocol includes reporting of incidence of type 2 diabetes mellitus and/or malignancies after
 cessation of r-hGH therapy

5.3.3 Criteria for Randomization or Initiation of Treatment with the Investigational Medicinal Product

Not applicable – this is a post-treatment observational study.

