8.3 Endpoints

8.3.1 Primary Endpoints

The number and proportion of subjects diagnosed at any time during the 10-year follow-up will be tabulated for the two primary endpoints:

- Type 2 diabetes mellitus
- Any malignancy

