9.1 Responsibilities of the Investigator

Investigators are responsible for screening and enrolling subjects into the study, for informing subjects of study process, for collecting subjects' demographic and medical data, for contacting the treating physician/GP when medical data is available, for following-up with the subjects at year 5 and 10 as well as for entering the relevant information into the eCRF for each subject.

Investigators will enrol subjects who have received Saizen® or other r-hGH products for the treatment of short stature due to SGA, as part of clinical studies or the post-marketing setting. Furthermore, Investigators will be encouraged to inform subjects who are still under r-hGH treatment about the EMR 200098 008/ SALTO study.

Even though patients will sign an ICF and enter into the study once r-hGH therapy is completed or permanently discontinued, the investigator will ask the subjects to provide a CICF while still on therapy, in order to allow the CRO's PMC to contact the subject and track subject contact information. The signature of the CICF is optional and will not limit the patient's participation in the SALTO study once eligibility criteria are met (see section 9.2).

As soon as the subjects complete or permanently discontinue treatment with Saizen® or other r-hGH products, the Investigators will be able to invite the subjects to participate in this observational study. At Sponsor's request he/she should obtain the written informed consent from the subject if he/she is an adult and also from the two parents or the legal guardian if he/she is minor. When minors reach the legal age, the Investigator will request written informed consent again. The Investigators will ensure that the subject's ICF will not be signed before these subjects have completed or have permanently discontinued or withdraw from r-hGH treatment (see also section 9.2).

Investigators will be also encouraged to re-contact or call back patients from their clinic who have permanently discontinued r-hGH treatment within a maximum of 5 years previously, in order to obtain consent to be enrolled into the study.

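### Subject-time runs from the last r-hGH dose although entry may come up to 5 years later, so part of each primary rate is conditional on survival and enrolment; a rate counted from consent should be shown beside it

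*Protocol*

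**What the plan says.** Four rules in the protocol combine.

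- **Entry (5.1):** "Subjects may be enrolled at any time from the day after their last r-hGH dose up until 5 years after treatment cessation". Section 7.1 requires a screening visit and Section 9.2 requires signed consent before any data are collected.
- **Time (8.5.2):** "The subject-time of follow-up will be defined as the time between the day of last r-hGH treatment and the end of the 10-year period".
- **Events:** Section 7.4.1.3 states that "The AE reporting period for safety surveillance is defined as the 10-year period after cessation of r-hGH treatment". Section 8.3.1 adds that "The number and proportion of subjects diagnosed at any time during the 10-year follow-up will be tabulated for the two primary endpoints". Section 7.1 fills the gap before consent: "any data of interest occurring from the time of permanent cessation of r-hGH therapy up to the signature of the ICF will be retrospectively collected".
- **How late entrants are found and screened:** under Section 9.1, "Investigators will be also encouraged to re-contact or call back patients from their clinic who have permanently discontinued r-hGH treatment" within the previous 5 years. Section 5.3.2 excludes "Patients enrolled in an interventional trial", with no exception for a trial entered because of an outcome that arose after the last dose.

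Section 8.6 applies the same analyses at 5 years. Section 8.5.2 leaves further detail to the SAP but fixes the definition of subject-time itself. The protocol calls the design both prospective and retrospective, but does not separate the two kinds of time in the primary analysis.

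**The concern.** A subject who consents 4 years after the last dose brings 4 years into the denominator during which that subject could not have died. A former patient who died of a malignancy in those years brings neither an event nor time. Counting from the last dose thus mixes follow-up that was watched forward with follow-up reconstructed in people who were later able to enrol.

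Two further routes may select on outcome. Call-back takes place when the clinic may already know the outcome. The interventional-trial exclusion could remove someone who is in a trial for a malignancy or diabetes at the time of screening.

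The study has no control group (5.1) and no significance testing (8.5.1). The incidence of these two outcomes is its main product, so a reader should be able to see how much of it rests on retrospective time.

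**Working it through.** The protocol gives no figure for entry lag or for the retrospective share, so there is no stated result to reproduce. The only numerical input on follow-up is the loss of up to 35% over 10 years (8.1).

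**Assumptions.** Entry lag L is (a) uniform over 0–2 years, (b) zero for half and uniform over 0–5 years for half, or (c) uniform over 0–5 years. Mean lags are 1, 1.25 and 2.5 years. The 35% who drop out do so uniformly between entry and year 10, and their time stops there.

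**Step 1: share of subject-time before consent at 10 years.** Mean observed time = 0.65 × 10 + 0.35 × (m + (10 − m)/2), with m the mean lag. Share s = m / mean observed time.

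| Lag | Mean time | Share |
|---|---|---|
| (a) | 8.43 | 1/8.43 = 12% |
| (b) | 8.47 | 1.25/8.47 = 15% |
| (c) | 8.69 | 2.5/8.69 = 29% |

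**Step 2: the same at the 5-year interim.** A subject who will drop out loses on average (5 − L)²/(2(10 − L)) years before year 5. Averaged over L this is 0.89, 0.87 and 0.48 years. Mean observed time = 5 − 0.35 × that loss = 4.69, 4.70 and 4.83 years. Shares: 1/4.69 = 21%, 1.25/4.70 = 27%, 2.5/4.83 = 52%.

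**Step 3: effect of fatal malignancies that can never enter.** With a constant, low event rate, expected events are proportional to time, so a share s of them falls before consent. If a fraction f of those is fatal before consent, observed/true rate ≈ 1 − f × s. The values of f are assumed; the protocol gives none.

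| Understatement | f = 10% | f = 20% | f = 40% |
|---|---|---|---|
| 10 years, (a) | 1.2% | 2.4% | 4.7% |
| 10 years, (b) | 1.5% | 3.0% | 5.9% |
| 10 years, (c) | 2.9% | 5.8% | 11.5% |
| 5 years, (a) | 2.1% | 4.3% | 8.5% |
| 5 years, (b) | 2.7% | 5.3% | 10.6% |
| 5 years, (c) | 5.2% | 10.4% | 20.7% |

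**Step 4: direction when all selection is considered.** Let r be the chance of enrolling after a pre-consent event relative to no event. With uniform 0–5 year entry and no drop-out (s = 2.5/10 = 25%), observed/true ≈ (1 − s) + r × s. This gives 0.75 at r = 0, about 0.87 at r = 0.5, 1.00 at r = 1 and 1.25 at r = 2. The protocol does not determine r.

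**Step 5: price of counting only from consent.** For 200 subjects followed to year 10, time from last dose is 200 × 10 = 2000 subject-years. From consent with uniform entry it is 200 × 7.5 = 1500. The one-sided 95% upper limit with zero events is −ln(0.05)/time, that is 1.50 against 2.00 per 1000 subject-years.

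**The case against.** A reader might go further than the documents allow in several ways.

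- **All pre-consent time is event-free by design.** It is not. Only death is impossible in it. Non-fatal diabetes and malignancy before consent are collected.
- **The malignancy rate is biased downward overall.** Fatal cases can only lower it, but survivors still attending the clinic may be easier to call back. The net direction is unknown for both endpoints.
- **Eligibility depends on the outcome.** No criterion names an outcome. The trial exclusion is worded as current enrolment, so someone whose trial ends inside the 5-year window is not barred by it. Its effect cannot be quantified.
- **The interim is wholly retrospective for late entrants.** That holds only for entry at exactly year 5.

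The defence has more substance on lag and on remedy. The optional contact consent during therapy and the invitation as soon as treatment ends (9.1, 9.2) favour short lags, for which the fatality effect is about 1 to 5% at 10 years.

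Replacing the from-cessation rate could also cost more than it gains. With 29% of time lost and a 10% bias, delayed entry lowers mean squared error only if 0.10² exceeds (1/E) × (1/0.71 − 1), where E is the number of expected events. That means E of about 41, or roughly 16 per 1000 in about 2,600 subject-years (300 × 8.69). It would also drop real safety events from the main rate, and the agreed commitment in Section 8.1 concerns 10 years after cessation.

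These arguments stand against making the delayed-entry rate the only primary result. They do not stand against showing it. The SAP is not at hand and may contain such an analysis, but one that followed Section 8.5.2 alone would not.

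**Conclusion.** The point holds in a limited form. Section 8.5.2 puts into the primary rates a block of time that is conditional on survival, contact and enrolment, and nothing in the protocol makes that block visible. Its size is about 12 to 29% of subject-years at 10 years and 21 to 52% at the interim, under assumed lags and 35% drop-out.

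The only effect whose sign is certain is the loss of fatal pre-consent malignancies. It is modest at 10 years, about 1 to 5% with the shortest lags and 3 to 12% with the longest, and reaches about 20% at the interim in the most extreme combination. Those figures rest on assumed fatal fractions of 10 to 40% and a constant rate. Selection through call-back and the trial exclusion could push either rate up or down. This is a cheap improvement in reporting, and it does not show that the planned rates are unusable.

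**What to change.** Amend Sections 8.5.2 and 8.6, and carry the change into the SAP. At both 5 and 10 years, report the incidence rates and cumulative incidence of type 2 diabetes and malignancy side by side:

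1. from the last dose, as now defined;
2. with each subject entering the risk set at the date of signed consent, keeping time since last dose as the time scale (left truncation).

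Tabulate pre-consent events and subject-years separately, and state that this part is conditional on survival and enrolment.

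**Cost.** Only the consent and last-dose dates are needed, and no data are discarded. The delayed-entry rate rests on about 12 to 29% fewer subject-years at 10 years and is less precise, which is why it accompanies the from-cessation rate and does not replace it. It has limits of its own: if the hazard is not constant, a crude truncated rate gives more weight to later years, and it does not remove selection on lasting risk factors. Changing the trial exclusion in 5.3.2 is not part of this fix. A subject with a pre-consent malignancy is no longer at risk of a first one at consent, so the change would add nothing to the left-truncated malignancy rate.
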